Primary Aim: The primary aim of this study is to determine the difference between changes in neurocognitive functioning from baseline to the 6 month follow-up in adult survivors of childhood cancer who are randomized to receive melatonin compared to those randomized to receive placebo. We hypothesize that survivors randomized to the melatonin group will have a greater improvement in neurocognitive functioning than those randomized to the placebo group. We have identified six neurocognitive domains in which the marginal impairment rate is >15% in the SJLIFE cohort. Normalized Z-scores ($M=0$, $SD=1$) are available for each domain and survivors who score at or below the 10th percentile will be classified as impaired on that specific domain. The lowest test-retest correlation coefficient for the neurocognitive measures has been observed to be 0.60. Then, assuming the difference in the Z-scores to be normally distributed but assuming (conservatively) the variance to be 1, we need outcome data for 131 survivors between the melatonin and placebo arms in Cohorts 1 and Group 2 to detect an improvement of .66 units (in standardized scale, considered to be clinically meaningful) with 80% power with type I error control $\alpha=0.05/6=0.0083$ to adjust for multiplicity of 6 tests for each subscale. The analysis for Aim 1 will be completed using a two-sample t-test. Assuming an attrition and loss to follow up of 25%, we plan to enroll 987 survivors (Cohort 1=328; Cohort 2=328; Cohort 3=331).

Protocol MNEMONIC and Title: MIND - Melatonin Intervention for Neurocognitive Deficits in the St. Jude Lifetime Cohort

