Secondary Aim 1: The primary interest of secondary aim one is to assess the efficacy of melatonin on delayed sleep onset latency in adult survivors of childhood cancer, which will be evaluated in Cohorts 2 and 3. We hypothesize that survivors randomized to the melatonin treatment arm will evidence a greater reduction in sleep onset latency compared to survivors randomized to placebo. The CCSS cohort mean and SD for sleep onset latency among participants with delayed sleep onset latency (i.e. SOL \geq 30 minutes) is 46.2 and 27.7 minutes, respectively. The test-retest correlation for sleep onset latency from the PSQI has been observed to be in the range of 0.70. Following the justification set forth in the Primary Aim, and assuming the SD to be 27.7, we will need outcome data for 131 survivors in Cohort 2 and 133 in Cohort 3 between the melatonin and placebo arms for these Cohorts to see an improvement of 15 minutes in sleep onset latency with 80% power with type I error control $\alpha=0.05$. The analysis for Aim 2 will be completed using a two-sample t-test.

Secondary Aim 2: The aim of this objective is to investigate the association between sleep onset latency and specific neurocognitive processes [Cohort 2]. We hypothesize that decreased sleep onset latency following 6 months of melatonin treatment will be associated with improved neurocognitive performance. We will need outcome data for 131 survivors in Cohort 2 [66 randomized to melatonin, 65 randomized to placebo] so that we will have 80% power to detect a correlation of at least 0.25 between reduced sleep onset latency and improved neurocognitive performance with type 1 error control $\alpha=0.05$.

Exploratory Aims: To explore the association between endogenous melatonin levels and improvement in sleep onset latency. To explore the association between sleep quality and psychological distress and health related quality of life.

Primary Anticipated Completion Date: [REDACTED]

Anticipated Study Completion Date: [REDACTED]

Timeframe for Primary Outcome Measure: Approximately 6 months

Data Management: Data will be managed by the Neuropsychology Research Team and the Clinical and Survey Research Center in the Department of Epidemiology and Cancer Control and the Department of Nursing Research. Statistical analysis will be provided by the Biostatistics Department at St. Jude Children's Research Hospital.

Human Subjects:

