Exogenous melatonin also has been demonstrated to promote sleep onset latency in healthy adult humans,⁴⁹ as well as adults with insomnia combined with dementia,⁵⁰ and mild cognitive impairment.⁴³ A meta-analysis on the efficacy of exogenous melatonin for primary insomnia reported reduced sleep onset latency of -7.2 minutes (95% CI -12.0 to -2.4).⁵¹ Efficacy has further been demonstrated in individuals with intellectual disabilities and autism spectrum disorder.⁵² Recent meta-

analyses of the effects of exogenous melatonin on sleep parameters reported decreased sleep latency of 23 and 34 minutes in individuals with delayed sleep phase disorder⁵³ and intellectual disabilities,⁵⁴ respectively. In a large randomized double blind placebo controlled trial, Wade and colleagues demonstrated significantly reduced sleep onset latency in adults 18-80 years of age over a six month trial, with a treatment effect of -6.8 minutes (95% CI -10.9 to -2.6).⁵⁵ Furthermore, their data demonstrated that treatment efficacy was independent of endogenous melatonin levels with no signs of tolerance or reduction in benefit during the 6-month treatment period.

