6.0 REQUIRED EVALUATIONS, TESTS, AND OBSERVATIONS

6.1 Pre-Screening Evaluations for Eligibility

Pre-screening will occur to determine eligibility prior to scheduling participants for their campus visit. If the participant appears eligible based upon telephone screening, a SJLIFE study visit will be scheduled. The remaining evaluations for study eligibility will occur prior to randomization on the study. All of the evaluations have been described in detail in section 4 above.

Baseline Measures: Baseline evaluation for all participants will include a medical evaluation, neurocognitive assessment, and collection of biological samples. Because evaluations performed, as detailed in the Children's Oncology Group "Long-Term Follow-Up Guidelines for Survivors of Childhood, Adolescent, and Young Adult Cancers," are standard care in the SJLIFE clinic, no additional monetary funds will be required for the baseline medical or neurocognitive evaluation in the proposed study cohort. Medical evaluations are based on primary cancer diagnosis, age at diagnosis, and therapeutic interventions and are limited to screening and diagnostic evaluations to characterize cancer-related health complications. Complete treatment records, including all information from all medical follow-up, will be available to study investigators. [name] is the Director of the SJLIFE clinic and carefully reviews and approves each abstracted treatment summary and medical history. The existing data give us the ability to carefully evaluate whether patients in our study are similar to or differ from nonparticipants. Table D summarizes the pre-screening evaluations and baseline measures.

Table D: Pre-screen and Baseline Measures

Evaluations – must be obtained prior to randomization	Prescreen	Baseline Visit
Inclusion/Exclusion criteria questions	X ¹	
Sleep-related questions		X
Informed consent		X
HIPAA		X
Standardized Sleep Measures		X
Melatonin		X ³
Correlative Psychosocial Measures		X ²
PRISE (side effect monitoring)		X
Neurocognitive Assessment Measures		X ²
Pregnancy Test**		X ²
History and Physical Exam		X ²

** The St. Jude IRB requires that a female patient of childbearing potential must have a negative pregnancy test as a condition of clinical research eligibility.

¹Mailed with introductory letter.

²Completed as part of SJLIFE protocol

³Optional

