11.0 STATISTICAL CONSIDERATIONS

The primary focus of this study is to evaluate the efficacy of melatonin on neurocognitive functioning in long term survivors of childhood cancer. Currently, there are 2,331 survivors potentially eligible for this study and 1,410 (61% have been identified as expected to have least one area of neurocognitive impairment. Further, it is estimated that among all the eligible survivors roughly 30% will have delayed sleep (sleep onset latency ≥ 30 minutes). Thus, the eligible survivors can be classified into three distinct cohorts (I) Those who are neurocognitively impaired but don't have delayed sleep 987 (II) Those who are neurocognitively impaired and have delayed sleep 423, i.e. 30% of 1,410, and (III) Those who don't have neurocognitive impairment but have delayed sleep problems (this would be roughly 30% (276) of those who are not neurocognitively impaired. Targeted enrollment for the study is 987 survivors and expected evaluable is 395.

[figure not shown]

Figure 2. Three group stratification with parallel allocation to melatonin/placebo

Primary Objective: Examine the efficacy of melatonin treatment on neurocognitive functioning in adult survivors of childhood cancer.

- Hypothesis 1: Long-term survivors of childhood cancer with documented baseline neurocognitive deficits (Cohorts 1 and 2), in attention, memory,

and/or executive functioning, randomized to the melatonin treatment arm, will demonstrate improved neurocognitive performance following six months of treatment compared to those randomized to placebo.

The primary objective of this study is to demonstrate that treatment with melatonin will be associated with improvement in neurocognitive performance. This will be evaluated in Cohorts 1 and 2 independently. The study will be conducted by randomizing survivors to melatonin or placebo within each of the two Cohorts.

For those who are in Cohorts 1 and 2 baseline neurocognitive evaluation along with other evaluations will be obtained prior to randomization to melatonin or placebo arm. After randomization, sleep data will be collected using actigraphy in week one when the survivors are in their homes. The intervention will be delivered for a period of six months with regular phone calls for monitoring. Then one week before the six month visit sleep data using actigraphy will be collected. The neurocognitive data will be collected at the 6 month return visit (post-treatment).

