There are 10 subscales on which a survivor could be impaired and, out of 10 such subscales, we have identified six in which the marginal impairment rates were seen to be greater than 15%. There are normalized Z-scores available for each subscale and a survivor that falls below the 10% (≤ -1.3) is classified as impaired on that subscale. It is possible that a survivor could be impaired on more than one subscale but we will assess improvement in each subscale independently. Thus, we will have the Z-score corresponding to each of the subscales within at baseline and at follow-up visit. For simplicity, consider the first subscale. We don't expect to see any change in the Z-scores for the placebo arm but we do expect to see an improvement in the melatonin arm. Let Z_{1m}^1 and Z_{2m}^1 denote the Z-scores at baseline and follow-up time points for the first subscale on melatonin arm and let Z_{1p}^1 and Z_{2p}^1 denote the Z-scores at baseline and follow-up time points for the first subscale in the placebo arm. Let $Z_{DM}^1 = Z_{2m}^1 - Z_{1m}^1$ and $Z_{DP}^1 = Z_{2p}^1 - Z_{1p}^1$ denote the difference between the two time points in the two arms. Then our interest is in testing the null hypothesis $H_0: \mu_{Z_{DM}^1} = \mu_{Z_{DP}^1}$ vs $H_1: \mu_{Z_{DM}^1} \neq \mu_{Z_{DP}^1}$ i.e. the mean of the difference scores for the first subscale would be same for the two arms vs. they will be different. The lowest test-retest correlation coefficient for the neurocognitive measures has been observed to be 0.60. Then, assuming the difference in the Z-scores to be normally distributed but assuming (conservatively) the variance to be 1, we will need to randomize 131 survivors between the melatonin and placebo arm to detect an improvement of 0.66 units (in standardized scale, considered to be clinically meaningful) with 80% power with type I error control $\alpha=0.05/6=0.0083$ to adjust for multiplicity of 6 tests for each subscale. However, the sample size required to evaluate the secondary objective in cohorts 2 and 3 is 131 and 133, respectively, per cohort. Thus, we plan to enroll 131 research participants from Cohorts 1 and 2 and 133 research participants from Cohort 3.

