The primary interest of Objective 2 is to assess the efficacy of melatonin on delayed sleep onset latency in adult survivors of childhood cancer, which will be evaluated in Cohorts 2 and 3. We hypothesize that survivors randomized to the melatonin treatment arm will evidence a greater improvement in sleep onset latency compared to survivors randomized to placebo. The CCSS cohort mean and SD for sleep onset latency among participants with delayed sleep onset latency (i.e. $SOL \geq 30$ minutes) is 46.2 and 27.7 minutes, respectively. The test-retest correlation for sleep onset latency from the PSQI has been observed to be in the range of 0.70. Following the justification set forth in Aim 1, and assuming the SD to be 27.7, we will need to randomize 131 and 133 survivors between the melatonin and placebo arms in Cohort 2 and Cohort 3, respectively, to see an improvement of 15 minutes in sleep onset latency with 80% power with type I error control $\alpha=0.05$. The analysis for Aim 2 will be completed using a two-sample t-test.

Secondary Objective: Investigate whether improvement in sleep onset latency due to melatonin treatment is associated with neurocognitive improvement in long-term childhood cancer survivors.

- Hypothesis 3: Improvement in sleep onset latency with melatonin treatment will result in improved neurocognitive performance in long-term childhood cancer survivors who have both comorbid sleep onset latency and neurocognitive deficits at baseline (Cohort 2).

The secondary interest of Objective 2 is to investigate the association between

sleep onset latency and specific neurocognitive processes in survivors with comorbid sleep and neurocognitive dysfunction [Cohort 2]. We hypothesize that decreased sleep onset latency following 6 months of melatonin treatment will be associated with improved neurocognitive performance. With a sample size of 131 in Cohort 2 [66 randomized to melatonin, 65 randomized to placebo] we will have 80% power to detect a correlation of at least 0.25 between reduced sleep onset latency and improved neurocognitive performance with type 1 error control $\alpha=0.05$.

Exploratory Objective: Explore the association between endogenous melatonin levels and improvement in sleep onset latency.

- Exploratory Hypothesis 1: Improvement in sleep onset latency following melatonin treatment will be independent of baseline endogenous melatonin levels.

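### The primary and sleep t-tests leave out the baseline covariate; ANCOVA on baseline values already collected would cut residual variance by about 10–20% (neurocognition) and 5–15% (sleep)

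*Combined protocol and SAP*

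**What the plan says.** **Primary aim.** The Protocol Summary (Data Analyses, Primary Aim) sets out to "determine the difference between changes in neurocognitive functioning from baseline to the 6 month follow-up" and continues: "The analysis for Aim 1 will be completed using a two-sample t-test". Section 11.0 defines the difference score (6 months minus baseline) in each arm and tests equality of the two means, two-sided, for each of six subscales, in Cohorts 1 and 2 separately. It adds: "The lowest test-retest correlation coefficient for the neurocognitive measures has been observed to be 0.60".

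**Sleep.** For Cohorts 2 and 3, Section 11.0 states: "The analysis for Aim 2 will be completed using a two-sample t-test". The Protocol Summary gives the correlation: "The test-retest correlation for sleep onset latency from the PSQI has been observed to be in the range of 0.70".

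**Covariates.** None is named for either test. Regression appears only under the exploratory objectives.

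**Availability of baseline.** Sections 3.6 and 11.0 place the neurocognitive baseline before randomization. Table D in Section 6.1 lists the standardized sleep measures at the baseline visit among evaluations that "must be obtained prior to randomization". Actigraphy differs. Section 11.0 says: "After randomization, sleep data will be collected using actigraphy in week one when the survivors are in their homes". Section 4.2 says only that the baseline sleep assessment precedes the start of the intervention.

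**The concern.** The change score does use the baseline, but it fixes the slope of follow-up on baseline at 1. With retest correlations of 0.60 and 0.70 and similar variances at the two visits, the true slope is well below 1, so part of the baseline noise is carried into the outcome. Estimating the slope removes that noise for one degree of freedom.

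Precision is at stake, not validity. Each primary and sleep comparison has a wider interval than the same participants could give. This matters most if the true effect is below the planning value. For sleep, Section 2.2.2 cites effects of 7.2 minutes (pooled, primary insomnia) and 6.8 minutes (a large 6-month trial), against a planned 15. It also cites 23 and 34 minutes in other populations.

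For sleep the plan also names neither the instrument that supplies the endpoint nor the value that serves as its baseline.

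**Working it through.** **Inputs from the protocol.** Neurocognition: lowest r = 0.60, planning variance of change 1, effect 0.66 SD, alpha 0.05/6 = 0.0083, N = 131 per cohort. Sleep: r ≈ 0.70 for PSQI latency (Section 4.2.3 gives 0.85 for PSQI test-retest reliability), SD 27.7 minutes, effect 15 minutes, alpha 0.05, N = 131 (Cohort 2) and 133 (Cohort 3). Power below is two-sided noncentral t with arms of 66 and 65, and 129 df (t-test) or 128 df (ANCOVA).

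**The plan's own figures.** At the stated inputs, 80% power needs 115 participants (primary) and 110 (sleep), not 131 and 131/133. With 131, power is 86.2% and 86.8%. That mismatch is a separate matter, because the percentage cut below depends on neither N nor alpha.

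**Variance cut, equal unit variances at both visits.**
- Change score: 2(1−r)
- ANCOVA residual: 1−r²
- Ratio: (1+r)/2, so the cut is (1−r)/2

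| r | Change | ANCOVA | Cut |
|---|---|---|---|
| 0.60 | 0.80 | 0.64 | 20% |
| 0.70 | 0.60 | 0.51 | 15% |
| 0.80 (assumed) | 0.40 | 0.36 | 10% |
| 0.85 | 0.30 | 0.2775 | 7.5% |

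A 20% cut is worth raising N from 131 to 131/0.8 ≈ 164; a 10% cut, to 131/0.9 ≈ 146. Intervals shorten by 1−√0.8 = 10.6% and 1−√0.9 = 5.1%.

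**Does selection on impairment undo this?** If the baseline variance within the cohort is v, the cut is (1−r)²v / [(1−r)²v + 1−r²]. Entry requires impairment on any one of six measures. Simulation of that rule (assumed inter-subscale correlation 0–0.4 and marginal impairment 10–20%) gives cuts of about 18–24% at r = 0.60 and 9–12% at r = 0.80. The cut would fall to 2–4% only if each test were limited to people impaired on that subscale (v ≈ 0.17). At r = 0.60, for example, 0.16×0.171/(0.16×0.171+0.64) = 4.1%. The plan sizes each subscale test on the whole cohort, so that is not the stated analysis.

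**Neurocognitive power, N = 131, alpha 0.0083, t-test → ANCOVA.**

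| r | 0.66 SD | 0.50 SD (assumed) |
|---|---|---|
| 0.60 | 93.7% → 97.8% | 69.8% → 81.3% |
| 0.70 | 98.5% → 99.5% | 84.3% → 90.6% |
| 0.80 | 99.9% → >99.9% | 96.6% → 98.1% |

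**Sleep, assuming the t-test is on change.** The SD of change is 27.7×√0.6 = 21.5 minutes. The ANCOVA residual SD is 27.7×√0.51 = 19.8, a 15% cut. If 0.70 is an unselected correlation, selecting the top 30% narrows the baseline. Under bivariate normality (assumed) the cut is then 4.5% if selection is on the measure itself, and 8.6–11.4% if it is on a variable correlated 0.8–0.6 with it. This gives the working range of about 5–15%.

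| True effect | t-test, SD 21.5 | ANCOVA, 5–15% cut | t-test, SD 27.7 | ANCOVA, 5–15% cut |
|---|---|---|---|---|
| 15 min | 97.8% | 98.3–99.1% | 86.8% | 88.4–91.6% |
| 10 min | 75% | 78–82% | 54% | 56–60% |
| 7.2 min | 48% | 50–54% | 31% | 33–36% |

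**The case against.** The strongest reply is that this is a preference about efficiency and not an error. The tests are valid, the change score already uses the baseline, and at the planned effects power rises only from 93.7% to 97.8% and from 97.8% to at most 99.1%. All of that is true, and it caps the weight of the point.

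Three objections to the size also stand in part:
- 0.60 is the lowest neurocognitive correlation, so 20% is roughly the ceiling. Subscales with higher r gain less, as the power table shows.
- The sleep figures are conditional. The plan only implies that the test is on change, the normality behind the range-restriction figures is doubtful for so skewed a measure, and at an SD of 27.7 power is lower throughout. Adjustment does not rescue a 7.2-minute effect under either SD. If 6-month values alone were compared, however, the saving at r = 0.70 would be r² = 49%, so assuming change is the cautious choice.
- The planned 15 minutes lies between the small and large effects that Section 2.2.2 cites, so a shortfall is possible but not established.

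On actigraphy, Section 4.2 leaves room for a first recording that follows randomization but precedes the first dose. Under blinding, such a recording could serve as a covariate. Sections 4.2 and 11.0 have to be reconciled before anyone relies on it.

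None of these objections gives a reason to prefer the fixed slope. In large samples the ANCOVA residual variance is never above that of the change score, and the two are equal only if the slope is 1.

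**Conclusion.** The point holds as an efficiency recommendation. The planned tests are unbiased but discard precision that the baseline data could supply: about 10–20% of residual variance for neurocognition and about 5–15% for sleep. The upper ends follow from the protocol's own correlations with equal variances at both visits. The 10% end for neurocognition assumes r = 0.80. The lower sleep values rest on the range-restriction assumptions, and the whole sleep range assumes a test on change. The practical benefit is small at the planned effects and useful if effects or accrual fall short. Adjustment also protects against chance baseline imbalance in arms of about 65. It should be adopted, but the trial's validity does not depend on it.

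**What to change.** **Primary.** For each subscale and cohort, fit ANCOVA of the 6-month Z-score on arm with the baseline Z-score as covariate, at the same alpha. Report the adjusted difference and its confidence interval. Keep the change-score t-test as a sensitivity analysis.

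**Sleep onset latency.** Name the measure to be tested and adjust for a pre-randomization baseline of that same measure, for example PSQI latency from the baseline visit. Do not use the actigraphy that Section 11.0 places after randomization as the covariate unless its timing is first reconciled with Section 4.2. A repeated-measures model with the 3- and 6-month values and a 6-month contrast is a reasonable alternative. Its benefit is mainly under dropout, which the plan puts at 25%.

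**Cost.** One degree of freedom per test and revised analysis wording in the Protocol Summary and Section 11.0, with no new data and no change in N. The protocol is already at Revision 4.3, so the change should be a dated amendment finalized before unblinding.

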 - a. Has neurocognitive impairment defined as performance on at least one measure of attention, memory, and/or executive functioning \leq 10th percentile.
 - b. Has delayed sleep onset latency defined as self-report of an inability to fall asleep within 30 minutes \geq once a week during the past month.
- Cohort 3 participant:**
 - a. Is absent of neurocognitive impairment defined as performance $>$ 10th percentile on all six measures of attention, memory, and executive functioning.
 - b. Has delayed sleep onset latency defined as self-report of an inability to fall asleep within 30 minutes \geq once a week during the past month.

Study Population:

Exclusion Criteria:

- 1) Known allergy to melatonin or any ingredients of the study product or placebo
- 2) Currently taking Melatonin
- 3) Known sleep apnea
- 4) Known medically treated sleep disorder (e.g. restless leg syndrome)
- 5) Known diabetes mellitus – insulin treated
- 6) Uncontrolled seizure disorder in the past 12 months
- 7) Reported current illicit drug or alcohol abuse or dependence
- 8) Reported current major psychiatric illness (i.e. schizophrenia, bipolar disorder)
- 9) Current treatment with:
 - a. Benzodiazepines or other CNS depressants
 - b. Fluvoxamine
 - c. Anticoagulants (e.g. Coumadin)
 - d. Immunosuppressant or corticosteroids
 - e. Nifedipine
- 10) Employed in a position that requires night work (i.e. 10pm to 6am)
- 11) Females who are pregnant or lactating/nursing
- 12) History of neurologic event unrelated to cancer or its treatment
- 13) Sensory impairment (vision, hearing) that prohibits completion of neurocognitive examination

Protocol MNEMONIC and Title: MIND - Melatonin Intervention for Neurocognitive Deficits in the St. Jude Lifetime Cohort

Sample Size: Targeted enrollment 987 and expected evaluable 395 research participants

- Cohort 1 = 131
- Cohort 2 = 131
- Cohort 3 = 133

Randomization:

Participants in each cohort will be randomized 1:1 to receive time release melatonin 3 mg or placebo daily for 6 months.

Data Analyses:

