3.3 Research Participant Recruitment

Recruitment: The study sample will be recruited from participants in the St. Jude Lifetime Cohort (SJLIFE) at SJCRH. This established survivor cohort includes all individuals diagnosed and treated at SJCRH during childhood who are now 10 or more years from diagnosis and are 18 years of age or older. Cohort participants receive risk-based medical follow-up care during their SJLIFE evaluation. Complete medical and treatment records for all survivors are available for review. Survivors undergo a neurocognitive evaluation as a part of the established SJLIFE parent

protocol. We will recruit survivors who previously underwent neurocognitive evaluation as a part of the parent protocol, as well as survivors who are eligible for future neurocognitive evaluation through SJLIFE.

As of June 6, 2012, 4,287 patients treated at SJCRH are eligible for participation in SJLIFE and 2,809 have agreed to return to the SJCRH campus for a SJLIFE evaluation. We propose to recruit 342 patients from the available sample, 232 with documented neurocognitive impairment and 110 without neurocognitive impairment. Between December 2007 and June 2011 we completed neurocognitive evaluations for 1,183 SJLIFE participants. Of these, 986 have a measured IQ >79 (83%). Sixty percent of patients with IQ >79 had observed impairment in ≥ 1 of the six neurocognitive domains required for inclusion in the current study. Based on sleep data obtained from the Childhood Cancer Survivor Study Cohort, we estimate that approximately 30% of survivors will have delayed sleep onset latency (SOL) ≥ 30 minutes once per week or more frequently. Figure 1 provides a schematic representation of expected study participants eligible for recruitment.

[figure not shown]

Figure 1. Flow diagram of expected study participants eligible for recruitment

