3.5 Enrollment on Study

A member of the study team will confirm potential participant eligibility as defined in Section 3.1-3.2, complete and sign the 'Participant Eligibility Checklist'. The study team will enter the Eligibility Checklist information into the Patient Protocol Manager (PPM) system. Initial eligibility will be reviewed, and a research participant-specific consent form will be generated. The complete signed Eligibility Checklist and consent/assent form(s) must be faxed or sent electronically to the CPDMO to complete the enrollment process.

The CPDMO is staffed 7:30 am-5:00 pm CST, Monday through Friday. A staff member is available at [REDACTED] for enrollment during the weekend.

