3.6 Procedures for Randomizing Research Participants

Once participants have completed baseline neurocognitive and sleep evaluations, they will be stratified into three cohorts. For stratification purposes the following definitions will apply:

- 1) **Neurocognitive impairment** will be defined as performance on at least one measure of attention, memory, and/or executive functioning ≤ 10 th

percentile. Performance will be measured using the following tests: Trail Making Test Part B, Digit Span Forward and Backward, Controlled Oral Word Association Test, California Verbal Learning Test-II (long delay free recall), and Conners' Continuous Performance Test-II (variability index).

2) **Absence of neurocognitive impairment** will be defined as performance >10 th percentile on all six measures of attention, memory, and executive functioning.

3) **Delayed sleep onset latency** will be defined as self-report of inability to fall asleep within 30 minutes \geq once a week during the past month.

4) **Absence of delayed sleep onset latency** will be defined as inability to fall asleep within 30 minutes $<$ once a week during the past month.

Each of the cohorts is described below:

Cohort 1:

- a. Has neurocognitive impairment defined as performance on at least one measure of attention, memory, and/or executive functioning ≤ 10 th percentile.
- b. Is absent of delayed sleep onset latency defined as an inability to fall asleep within 30 minutes $<$ once a week during the past month.

Cohort 2:

- a. Has neurocognitive impairment defined as performance on at least one measure of attention, memory, and/ or executive functioning ≤ 10 th percentile.
- b. Has delayed sleep onset latency defined as self-report of an inability to fall asleep within 30 minutes \geq once a week during the past month.

Cohort 3:

- a. Is absent of neurocognitive impairment defined as performance >10 th percentile on all six measures of attention, memory, and executive functioning.
- b. Has delayed sleep onset latency defined as self-report of an inability to fall asleep within 30 minutes \geq once a week during the past month.

Upon completion of baseline neurocognitive and sleep evaluations, if it is determined that the participant does not have neurocognitive impairment and no delayed sleep onset latency, he or she will not be randomized and will be taken off study.

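### The enrolment target of 987 does not follow from the stated 25% loss (395 evaluable would need 528), and Section 11.0 reuses the evaluable numbers as numbers to randomise or enrol

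*Combined protocol and SAP*

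**What the plan says.** - **Enrolment and its basis.** The Protocol Summary (Data Analyses, Primary Aim) states: "Assuming an attrition and loss to follow up of 25%, we plan to enroll 987 survivors (Cohort 1=328; Cohort 2=328; Cohort 3=331"). No other basis for 987 is given anywhere.
- **Evaluable numbers.** The Summary's Sample Size entry reads "Targeted enrollment 987 and expected evaluable 395 research participants", split 131/131/133. The opening of Section 11.0 repeats 987 and 395. The Primary Aim text describes 131 as people with data: "we need outcome data for 131 survivors between the melatonin and placebo arms in Cohorts 1 and Group 2". Secondary Aim 1 does the same for 131 and 133. Secondary Aim 2 asks for "outcome data for 131 survivors in Cohort 2 [66 randomized to melatonin, 65 randomized to placebo"].
- **The same numbers with another meaning.** The primary objective text of Section 11.0 says 131 are to be randomised, and then that 131 from Cohorts 1 and 2 and 133 from Cohort 3 are to be enrolled. The sleep latency text says 131 and 133 are to be randomised. Neither allows for loss.
- **A third set of counts.** Section 3.3 says: "We propose to recruit 342 patients from the available sample, 232 with documented neurocognitive impairment and 110 without neurocognitive impairment". The Section 11.2 table lists 232 participants for objective 1.1 and 226 for objective 2.1, beside 131 and 395 in other rows.
- **Order of events.** Consent is taken at the screening-measures visit (Section 12.0). The signed checklist and consent "must be faxed or sent electronically to the CPDMO to complete the enrollment process" (Section 3.5). Section 3.6 then says: "Once participants have completed baseline neurocognitive and sleep evaluations, they will be stratified into three cohorts". For a person found to have neither condition, "he or she will not be randomized and will be taken off study".

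**The concern.** An enrolment target should follow from the evaluable number and the stated loss. Here 25% is the only stated loss, and it does not connect 395 to 987. The number to randomise is therefore neither stated consistently nor derivable: a reader could arrive at 395, 528 or anything up to 987.

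The error could matter in either direction. If the trial randomised only 131/131/133, as the objective text of Section 11.0 says, ordinary attrition would take it below its own evaluable targets. If 987 were taken as the number to randomise, the trial would treat 459 more people than 25% loss justifies (987 − 528).

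**Working it through.** **Inputs.** Evaluable 131/131/133 (Summary, Sample Size). Loss 25% and enrolment 328/328/331 (Summary, Primary Aim). Primary test: difference 0.66, variance 1, α = 0.05/6, two-sided. Sleep latency: difference 15 minutes, SD 27.7, α = 0.05. Correlation 0.25, α = 0.05. Test-retest correlations 0.60 and 0.70.

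**1. Trying to reproduce 987.** Enrolled = evaluable / (1 − loss).
- 131/0.75 = 174.7, so 175 (Cohorts 1 and 2)
- 133/0.75 = 177.3, so 178 (Cohort 3)
- Total 175 + 175 + 178 = 528; pooled, 395/0.75 = 526.7, so 527

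The plan's 987 is 987/528 = 1.87 times this. Other readings of 25% also fail. Multiplying by 1.25 gives 164 + 164 + 167 = 495. Compounding 25% over two, three or four stages gives 702, 936 or 1,248.

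**2. What the stated figures imply.** 131/328 = 39.9%, 133/331 = 40.2% and 395/987 = 40.0% evaluable, so about 60% are not evaluable in every cohort. Conversely, 987 × 0.75 = 740 (246/246/248) would be evaluable at 25% loss, not 395.

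**3. If 987 counts people consented** and 25% is loss after randomisation, then 987 − 528 = 459 people, or 459/987 = 46.5%, are never randomised. No such rate is stated.

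**4. Conditional power.** Suppose only 131 or 133 are randomised and 25% are lost: 131 × 0.75 ≈ 98 and 133 × 0.75 ≈ 100 remain. The t-tests use the noncentral t and the correlation uses Fisher's z.

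| Test | Power at 131 or 133 | Power at 98 or 100, stated variance | Power at 98 or 100, variance from test-retest r |
|---|---|---|---|
| Primary, per subscale | 86.2% | 71.5% | 82.8% |
| Sleep latency, Cohort 2 | 86.8% | 75.6% | 92.9% |
| Sleep latency, Cohort 3 | 87.3% | 76.5% | 93.3% |
| Correlation 0.25 | 82.4% | 70.2% | 70.2% |

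The last column uses change variance 2(1 − 0.60) = 0.80 for the primary test and change SD 27.7 × √(2(1 − 0.70)) = 21.5 for sleep latency. The correlation does not depend on these.

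**5. The counts in Sections 3.3 and 11.2.** With equal arms, 58 per arm (116) gives 80.6% for the primary test and 55 per arm (110) gives 80.4% for sleep latency. Then 116 + 116 = 232, 116 + 110 = 226, and 116 + 116 + 110 = 342. These are exactly the figures in those two sections. The current set gives 131 + 131 = 262, 131 + 133 = 264, and 395. Two sets of sample sizes therefore stand in the current text.

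**The case against.** The strongest defence is that enrolment precedes randomisation in this trial. Consent and the checklist complete enrolment; testing, cohort assignment and removal of people with neither condition come later. So 987 may count people consented, and 60% would then mix people never randomised with people lost afterwards. The split into 328/328/331 could be by expected cohort, since the Summary says initial eligibility uses earlier test data and telephone screening.

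This stands as a possibility, and 60% should not be read as a post-randomisation dropout rate. It does not rescue the text. The plan attributes 987 to attrition and loss to follow-up alone and states no not-randomised rate. It also does not say that the split is by expected cohort, although people with neither condition belong to none and 328 + 328 + 331 already uses up all 987.

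Other points on that side have weight:
- The power loss is conditional. It needs the objective text of Section 11.0 to be followed literally, against that section's opening paragraph, and with the smaller change variance both t-tests stay above 80%.
- In Secondary Aim 2, the words about 66 and 65 randomised may only name the arms of people with data. That is a minor wording point.
- Evaluable is not defined. Participants who cannot return at 6 months complete a mailed questionnaire (Section 6.3), and the plan does not say whether the 25% covers them. The 528 rests on the 25% being all of the loss after randomisation.

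None of this explains how 25% gives 987.

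**Conclusion.** The concern holds, and the text needs correcting before the figures are relied on. At the stated 25% loss, 395 evaluable requires 528, not 987. The stated pair leaves 40% evaluable, and no second rate bridges the difference. If 987 counts people randomised, either 987 or the 25% is wrong. If it counts people consented, 25% is not its basis and a not-randomised rate of about 47% is missing. Separately, Section 11.0 contradicts both its own opening paragraph and the Summary on whether 131 and 133 are evaluable, randomised or enrolled.

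The arithmetic uses only the plan's figures. Which reading of 987 is intended cannot be settled from the documents. The fall in power is conditional on randomising only 131/131/133. Under the smaller change variance it is confined to the correlation (70.2%). Planned power at 395 evaluable is unaffected.

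**What to change.** 1. State whether 987 counts people consented or randomised, and how it was derived. Section 11.0 also gives 987 as the number eligible for Cohort 1 (1,410 − 423); say whether the match is a coincidence.
2. Give consented, randomised and evaluable targets for each cohort, with the loss assumed at each step, and define evaluable. If 25% is confirmed as the whole loss after randomisation, the randomised targets are 175/175/178 (528). Any excess up to 987 then needs a stated and justified not-randomised rate, about 47% overall. If 987 counts people randomised, correct 987 or the 25%.
3. Say whether 328/328/331 is by expected or assigned cohort. Explain 331 for Cohort 3 against the 276 currently eligible in Section 11.0. This is not shown to be impossible, because Section 3.3 also recruits survivors who become eligible for testing later.
4. In the primary and sleep latency text of Section 11.0, describe 131 and 133 as evaluable. In both places where 66 and 65 appear (Summary, Secondary Aim 2, and Section 11.0), call them evaluable per arm.
5. In Section 11.2, change 232 to 262 and 226 to 264. In Section 3.3, replace 342 (232 + 110) with 395 (262 + 133) if it counts evaluable people, or with the agreed enrolment total if it counts people recruited.

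The cost is a text correction in the Summary and Sections 3.3, 11.0 and 11.2. The evaluable targets and the analysis do not change. Whether the enrolment number changes depends on the answers to items 1 and 2.
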